#### 219112 (MRNA CLINRES-001) Protocol Amendment 3 Final

Type of contact	Screening	Visit 1	TC1*	Visit 2	Visit 3	Visit 4	TC2	Visit 5				
Time points	period	D1	D2	D8	D15	D31	M3	M6	Early	Unscheduled	Unscheduled cardiac evaluation	
Window (D)	D-14 to -1	0	0	+2	±2	±3	±5	±7				Notes
Assessment and sampling time	Pre-Vacc	Pre-	Post-	Post-	Post-	Post-	Post-	Post-	termination	COVID-19		
points		Vacc	Vacc	Vacc	Vacc	Vacc	Vacc	Vacc				
Laboratory assessment												
SARS-CoV-2 N protein serology		•			•	•		•	•			Section 8.2.1
SARS-CoV-2 RT-PCR												Section 8.2.1
(nasopharyngeal swab)	•	•		•	•					•		
Blood sample for binding IgG		٠			•	٠		•	•			Section 8.2.1
Blood sample for neutralization		•			•	٠		•	•			Section 8.2.1
Blood sample for PBMC ICS assay preparation		•			•	•		•	•			Section 8.2.1
Safety assessments			•		•							
Hematology and serum chemistry	•	•		•	•						•	Section 8.3.6
Cardiac troponin I	•			•							•	Section 8.2.1
Record any concomitant medication/vaccination	•	•		•	•	•	•	•	•	•		Section 6.8
Record solicited AEs in eDiary (up to 7 days after vaccination)		0		0								Section 8.4
Record unsolicited AEs (up to 30 days after vaccination)		•	•	•	•	•						Section 8.4
Reporting of SAEs, MAAEs, AESI (including COVID-19), and pregnancies		•	•	•	•	•	•	•	•	•	•	Section 8.4
Recording of SAEs related to study participation, or to a concurrent GSK medication/vaccine	•	•	•	•	•	•	•	•	•	•	•	Section 8.4
EKG	•			•							•	Section 8.3.4
Study Conclusion								•	•			

AE: Ádverse event; AESI: Adverse events of special interest; D: Day; eCRF: electronic Case report form; eDiary: electronic Diary card; EKG: Electrocardiogram; GSK: GlaxoSmithKline Biologicals SA; ICS: Intracellular cytokine staining; IgG: Immunoglobulin G; M: Month; MAAE: Medically attended adverse event; N: Nucleocapsid; PBMC: Peripheral blood mononuclear cell; pIMD: potential Immune-mediated disease; RT-PCR: Real-time polymerase chain reaction; SAE: Serious adverse event; TC: Telephone call; Vacc: Vaccination.

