# 5.2.1. Medical conditions

- Has a new onset, clinically significant, abnormal biochemistry or hematology finding (defined as ≥Grade 1) at screening (participants with Grade 1 laboratory abnormalities that have been stable for at least 6 months before enrollment may be included in the study).
- 2. Has any medical disease or condition that, in the opinion of the investigator, precludes study participation. This includes any acute, subacute, intermittent, or chronic medical disease or condition that would place the participant at an unacceptable risk of injury, render the participant unable to meet the requirements of the protocol, or may interfere with the evaluation of responses or the participant's successful completion of the trial.
- 3. Any confirmed or suspected immunosuppressive or immunodeficient condition, based on medical history and physical examination (no laboratory testing required).

- 4. History of myocarditis, pericarditis, second and third degree heart block or idiopathic cardiomyopathy, or presence of any medical condition that increases risk of myocarditis or pericarditis, including cocaine abuse, cardiomyopathy, endomyocardial fibrosis, hypereosinophilic syndrome, hypersensitivity myocarditis eosinophilic granulomatosis with polyangiitis, persistent myocardial viral infection (e.g., due to enterovirus or adenovirus).
- 5. Has an acute febrile illness with a temperature ≥38.0°C or ≥100.4°F observed by the participant or at the study site within 72 hours prior to study vaccination. Participants with suspected COVID-19 symptoms (Section 8.4.4.2.2) should be excluded and referred for medical care.
- 6. Has a history of hypersensitivity or severe allergic reaction, including anaphylaxis, generalized urticaria, angioedema, and other significant reactions to any previous vaccine, or any component of the study vaccine.
- 7. Has a body mass index  $>40 \text{ kg/m}^2$ .
- 8. Has had known close contact with anyone who had a confirmed SARS-CoV-2 infection within 14 days before study vaccination.
- 9. Has a history of documented SARS-CoV-2 infection or COVID-19 within 6 months before the date of screening visit.
- 10. Has any self-reported or medically documented clinically significant medical or psychiatric condition. Significant medical conditions include, but are not limited to, the following:
  - a. Moderate or severe respiratory disease (e.g., chronic obstructive pulmonary disease, asthma).

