## 8.4.4.2.2. SARS-CoV-2 infection and COVID-19 definitions and assessment

Vaccine efficacy will not be evaluated in this study, but all laboratory-confirmed asymptomatic SARS-CoV-2 infections should be reported by the participant and documented as AEs, while virologically confirmed cases of COVID-19 are reported as AESIs. Any available isolate genotyping results will also be requested. Participants will be instructed to inform the investigator in the event of a positive SARS-CoV-2 diagnostic test. Serology testing for SARS-CoV-2 N protein will be performed pre-vaccination and post-vaccination to monitor for undetected SARS-CoV-2 infections at the time points specified in the SoA (Section 1.3).

All participants with suspected COVID-19 are required to have an unscheduled visit for suspected COVID-19, as detailed in the SoA (Section 1.3). At this visit, participants will undergo the following assessments:

- Medical history
- SARS-CoV-2 RT-PCR (nasopharyngeal or mid-turbinate swab)
- Physical examination
- Vital sign measurements
- Body temperature
- Review of AEs
- Concomitant medication/vaccination

All participants with confirmed COVID-19 are required to have an unscheduled COVID-19 convalescent visit as detailed in the SoA (Section 1.3). At this visit, participants will undergo the following assessments:

- Medical history
- SARS-CoV-2 RT-PCR (nasopharyngeal or mid-turbinate swab)

- Physical examination
- Vital sign measurements
- Body temperature
- COVID-19 evaluation
- Review of AEs
- Concomitant medication/vaccination

To complete the COVID-19 evaluation, the investigator will review the history of the participants, including medical records to define the severity of COVID-19.

Any confirmed cases of SARS-CoV-2 infection or COVID-19 during the study will be assigned one of the following definitions and recorded in the eCRF:

Asymptomatic SARS-CoV-2 infection:	Laboratory-confirmed SARS-CoV-2 by RT-PCR or SARS-CoV- 2 N protein seroconversion without any of the following symptoms: fever or chills, cough, shortness of breath or difficulty breathing, fatigue, muscle or body aches, headache, new loss of taste or smell, sore throat, congestion or runny nose, nausea or vomiting, diarrhea		

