## 4.3.2. Immunogenicity

#### 4.3.2.1. Analysis of immunogenicity planned in the protocol

The analysis of the secondary immunogenicity endpoints will be performed on the PPS. The descriptive summary will consist in the number of results available (N), standard deviation, median, interquartile, minimum, and maximum, GMT or GMR, and associated 95% CIs. For the analysis of immunogenicity, missing or non-evaluable measurements will not be replaced. Therefore, a participant will be excluded from an analysis if all measurements are missing or non-evaluable.

If more than 10% of participants with BA.5 immunogenicity data at Day 15 are eliminated from any of the PPS in any treatment group, a sensitivity analysis will be carried out using the Exposed Set.

Secondary Immunogenicity Endpoints	Statistical Analysis Methods
Neutralizing titer against pseudovirus bearing S protein from vaccine encoded SARS-CoV-2 and WT strains at each collection timepoint (D1, D15, D31, M6).	Neutralizing titer (GMT) against pseudovirus bearing S protein from vaccine encoded SARS-CoV-2 and WT strains will be tabulated with 95% CI at baseline and each post vaccination visit by treatment. The 95% CI will be calculated based on the t-distribution of the log- transformed value of GMT, then back-transformed to the original scale for presentation with the assumption that log-transformed concentration is normally distributed with variance specific to each treatment group. Bar charts (including 95% CIs) of GMT in log10 scale at
	each visit by treatment will be provided. At each post vaccination timepoint, the adjusted GMTs of neutralizing titer, with their 95% CI, will be obtained using an ANCOVA model on log10 transformed titers with treatment group as a fixed factor, and log10 transformed Day 1 baseline value as a covariable.
	Once Part B data are available, Part A and Part B data will be pooled together for model based analyses. When pooled, the study part will be added as a fixed factor and adjusted GMT will be estimated under Part A condition. Groups common in Part A and Part B will be combined as one group respectively for the pooled analysis. Outputs will be displayed by 3 $\mu$ g, 10 $\mu$ g, 30 $\mu$ g, 100 $\mu$ g, and pooled placebo.
	Listing of neutralizing titers sorted by treatment and participant number will be provided.

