GMR from baseline (D1) of neutralizing titer against pseudovirus bearing S protein from vaccine encoded SARS-CoV-2 and WT strains at each collection timepoint.	GMR from baseline of neutralizing titer against pseudovirus bearing S protein from vaccine encoded SARS-CoV-2 and WT strains will be tabulated with 95% CI at each post vaccination visit by treatment. The 95% CI will be calculated based on the t-distribution of the log-transformed fold rise value for GMR, then back- transformed to the original scale for presentation. Bar charts (including 95% Cls) of GMR in log2 scale at
	each post vaccination visit by treatment will be provided. At each post vaccination timepoint, the adjusted GMRs from baseline of neutralizing titer, with their 95% CI, will be obtained using an ANCOVA on log10 transformed

Secondary Immunogenicity Endpoints	Statistical Analysis Methods
	titers with treatment group as a fixed factor, and log10 transformed Day 1 baseline value as a covariable. Once Part B data are available, Part A and Part B data will be pooled together for model based analyses. When pooled, the study part will be added as a fixed factor and adjusted GMR will be estimated under Part A condition. Groups common in Part A and Part B will be combined as one group respectively for the pooled analysis. Outputs will be displayed by 3 µg, 10 µg, 30 µg, 100 µg, and pooled placebo.
	In addition, the similar ANCOVA model for GMR from baseline will be performed to further evaluate the linear dose effect, using dose level as a continuous variable.
Vaccine response rate based on neutralizing titers against vaccine encoded SARS-CoV-2 and WT strains at each collection timepoint.	The number and percentage with exact 95% CI of participants with vaccine responses of at least a 2, 4, and 8 fold increases from Day 1 baseline, with their exact 95% CI will be tabulated by treatment and visit.

The following SAS code will be used to calculate GMT/GMR from baseline, where LOGVAL is the log10 transformed GMT/GMR values at each post vaccination point, and Base is log10 transformed pre-dose GMT value. The analyses will be performed on PPS only.

```
Proc sort data = study; by group step; run; /** group will be sorted with order of Placebo, 3, 10, 30, 100***/;
```

```
proc MIXED data=study;
```

```
class group (ref='Placebo') step (ref='1'); /**step='1' indicates Part B, base=log pre-vaccination titer**/;
model LOGVAL = BASE group step/ solution noint;
```

	-	

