estimate 'Placebo'	base X	group 0 0 0 0 1 step 1 0/ cl;
estimate '3'	base X	group 1 0 0 0 0 step 1 0/ cl;
estimate '10'	base X	group 0 1 0 0 0 step 1 0/ cl;
estimate '30'	base X	group 0 0 1 0 0 step 1 0/ cl;
estimate '100'	base X	group 0 0 0 1 0 step 1 0/ cl;
de output actimatac=a	stmenolin	

ods output estimates=estmrnalin;

quit;

```
where X is GMT at pre-dose across groups for Part A.
```

The following SAS code will be used to further evaluate the linear dose effect on GMR from baseline of neutralizing titer against pseudovirus bearing S protein from vaccine encoded SARS-CoV-2 and WT strains, where LOGVAL is the log10 transformed GMR values at each post vaccination point, and Base is log10 transformed pre-dose titer value. The analyses will be performed on PPS only.

```
proc MIXED data=study;
```

class step (ref='1'); /**step='1' indicates Part B, base=log pre-vaccination titer**/;			
model LOGVAL = BASE dose step/ solution;			
estimate	'Placebo'	intercept 1 base X dose 0	step 1 0/ cl;
estimate	'3'	intercept 1 base X dose 3	step 1 0/ cl;;
estimate	'10'	intercept 1 base X dose 10	step 1 0/ CL;
estimate	'30'	intercept 1 base X dose 30	step 1 0/ CL;
estimate	'100'	intercept 1 base X dose 100	step 1 0/ CL;
ods output estimates=estmrnalin;			
quit;			
where X is GMT at pre-dose across groups for Part A.			

Geometric mean ratios (GMRs) will be computed at each sampling timepoint after dosing versus baseline (D1). The GMRs and 95% Cis will be constructed by exponentiating (base 10) the means of within-participant differences between log-transformed titers after each sampling timepoint and log-transformed titers at baseline. GMR will be calculated only for participants with valid baseline immunogenicity results.

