## 6.1.2. Demographic and Baseline Characteristics

#### 6.1.2.1. Analysis of demographics/baseline characteristics

These analyses will be performed on the Exposed set and PP set at Day 15, Day 31.

The demographic characteristics including height, weight, body mass index (BMI), age at screening in years, sex, race, ethnicity, and N protein) will be summarized by treatment using descriptive statistics.

- Frequency tables will be generated for categorical variable such as sex, race and ethnicity.
- Mean, median, standard error and range will be provided for continuous data such as age, height, weight and BMI.

The distribution of participants will be tabulated as a whole and per treatment group.

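### Day 1 anti-N status is collected but left out of the dose ANCOVAs; if prior infection alters response at equal baseline titer, adjusted dose ratios could shift modestly, chiefly for 100 µg

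*Protocol*

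**What the plan says.** **Collection.** Protocol 1.3 (Table 1) lists "SARS-CoV-2 N protein serology" at Day 1, Day 15, Day 31 and Month 6, and Protocol 8.2.1 and 8.2.3 apply it to all enrolled participants. Its stated purpose is surveillance (Protocol 8.4.4.2.2): "Serology testing for SARS-CoV-2 N protein will be performed pre-vaccination and post-vaccination to monitor for undetected SARS-CoV-2 infections".

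**Eligibility.** The relevant exclusion (Protocol 5.2.1) is "Has a history of documented SARS-CoV-2 infection or COVID-19 within 6 months before the date of screening visit". Older or undocumented infection can therefore enter.

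**Models.** SAP 4.3.2.1 specifies the ANCOVA "with treatment group as a fixed factor, and log10 transformed Day 1 baseline value as a covariable". For the pooled analysis, "the study part will be added as a fixed factor and adjusted GMT will be estimated under Part A condition". The SAS code agrees: "model LOGVAL = BASE group step/ solution noint" for dose groups and "model LOGVAL = BASE dose step/ solution" for linear dose. SAP 4.4.1.1 uses the same terms for IgG. Anti-N status appears in none of them, and SAP 4.7.1 plans no subgroup analysis.

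**Baseline table.** SAP 6.1.2.1 summarizes "age at screening in years, sex, race, ethnicity, and N protein" by treatment, on the Exposed Set and on the PP set at Day 15 and Day 31. It gives no rule for what follows if groups differ.

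**Allocation.** In Part A (Protocol 1.2, 6.3.3) randomization is 3:1 vaccine to placebo within each dose group. Groups 1 and 2 enroll in parallel; Group 3 starts after the Day 8 safety review of their sentinels (Protocol 4.1, 8.3.7.1). Part B randomizes 3 µg, 10 µg and placebo 3:3:1.

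**The concern.** Each dose group can mix participants with and without earlier infection. Baseline titer carries the part of that history that acts through pre-dose antibody. It cannot separate two participants with the same Day 1 titer, one from infection and one from vaccination alone, if they respond differently to a further dose. Any such remaining difference goes into the dose estimate whenever the groups differ in their share of previously infected participants.

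With about 16 evaluable vaccinees per dose, chance alone produces some imbalance. For 100 µg there is a second route: enrollment is later and no randomization between dose groups is described, so the share could differ systematically. Study part separates Part A from Part B, not 100 µg from 10 and 30 µg within Part A. Protocol 9.2 says the trial's size was set with dose decisions in mind, and the adjusted GMTs, GMRs and linear dose model are the estimates that will be read for that purpose.

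**Working it through.** **1. The plan's own precision figure (Protocol 9.2, SAP 5).** Inputs: n = 16, SD 0.45 log10, two-sided 95%. 10^(t(0.975, 15) × 0.45/√16) = 10^(2.131 × 0.1125) = 1.737, which reproduces the stated 1.74.

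**2. Precision of a ratio of two doses, same inputs.** SE = 0.45 × √(2/16) = 0.159 log10. Half-width = 10^(2.042 × 0.159) = 2.11-fold.

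**3. Assumptions, not in the documents.** Anti-N prevalence 50% to 85%; effect of anti-N status at equal baseline titer 0.2 to 0.3 log10 in vaccinees, of either sign; anti-N positivity raises baseline titer by 0 or 0.3 log10.

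**4. Chance of a gap of at least 20 points (exact binomial, both groups at the same prevalence).**

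| Comparison | 50% | 70% | 85% |
|---|---|---|---|
| 16 vs 16 (for example 30 vs 100 µg) | 21.5% | 17.5% | 8.0% |
| 32 vs 16 (pooled 10 µg vs 30 or 100 µg) | 18.5% | 14.7% | 6.1% |

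For some pair among the four doses (16/32/16/16) to differ by at least 25 points, the chance is 52%, 44% and 31% at prevalence 50%, 70% and 80%.

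**5. Size of the shift.** Shift ≈ residual effect × gap.
- 0.2 × 0.20 = 0.04 log10, a ratio of 10^0.04 = 1.10.
- 0.3 × 0.25 = 0.075 log10, a ratio of 1.19.
- Simulating the pooled per-protocol design (16 per vaccine cell) gives a mean error of about 0.04 to 0.08 log10 when the gap is at least 20 points. This is 0.04/0.159 = 0.25 to 0.08/0.159 = 0.5 of a standard error.
- In a two-group check with 12/16 vs 8/16 positive and no true dose effect, the planned model gave a ratio of 1.04 to 1.07, 1.09 to 1.13 and 1.14 to 1.19 for residual effects of 0.1, 0.2 and 0.3. With anti-N added it gave 0.99 to 1.02. With a residual effect of zero the planned model was already at about 1.00.

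**6. Average gain for 10 vs 30 µg.** Across random imbalances, RMSE falls by about 0.1% to 4% at effects of 0.2 to 0.3. With no residual effect, adding anti-N costs under 1%.

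**7. Systematic drift in the 100 µg group (60% vs 85% positive, assumed).** Expected bias = 0.25 × 0.2 = 0.05 to 0.25 × 0.3 = 0.075 log10. Simulation gives about 0.07 at an effect of 0.3; adding anti-N reduces it to 0.00 to 0.02 and RMSE by about 9%.

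**8. Coverage of the planned intervals.** With a common prevalence, 0.946 to 0.955. With 60% vs 85%, about 93% to 95%.

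**9. Against placebo, effect in vaccinees only.** For 10 µg vs placebo, a single common anti-N term changed RMSE by between -0.4% and +1.1%: no useful gain.

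**The case against.** The strongest reply is that the premise comes from outside the documents. No section says that anti-N status alters response at equal titer, and Day 1 titer is already in every model. With no residual effect there is no bias. That stands, and it makes the point conditional.

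The shift is also small beside a 2.1-fold half-width, the analyses are descriptive, and the planned intervals keep close to nominal coverage. All true. A reader might infer that the planned ANCOVA is invalid, or that imbalance will be mistaken for a dose effect; neither follows.

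An imbalance would be visible in the baseline table. Yes, but a table does not correct the adjusted estimates. A covariate chosen after seeing it would be data-driven, and the sponsor's statistical team is unblinded after the Part A Day 15 analysis (SAP 4.8.1).

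A reader might also infer that the Part A dose groups are confounded by prior infection. The documents show only that no randomization between them is described and that Group 3 comes later. They do not show that prevalence differs. The Part B comparison of 3 with 10 µg is randomized.

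Finally, covariate choice is a judgement, and the amendment history shows that other immune-history covariates were considered and replaced. That is fair, and it is why a supportive model is an acceptable minimum.

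**Conclusion.** The omission is real: a baseline marker of prior infection is collected from everyone, tabulated, and used in no dose model. Its consequence is conditional and modest. If the residual effect is 0.2 to 0.3 log10, a gap of 20 points or more moves an adjusted dose ratio by about 0.04 to 0.08 log10. For 10 vs 30 µg in the pooled design, such a gap arises by chance in about 6% to 19% of trials. The clearest exposure is 100 µg against 10 and 30 µg, where drift in prevalence would give a bias that neither study part nor the baseline table removes. Prevalence, effect size and sign are all assumptions, so the point supports a low-cost prespecified adjustment. It does not support a claim that the planned results would mislead.

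**What to change.** - In SAP 4.3.2.1 and 4.4.1.1, add Day 1 anti-N status (positive or negative) as a fixed covariate in the group ANCOVAs for GMT, GMR and GMC and in the linear dose model. At minimum, prespecify this as a supportive analysis reported beside the planned one.
- State the anti-N cut-off, since the LLOQ table following SAP 6.2.3.5 has no anti-N entry, and give a rule for a missing Day 1 result.
- State the anti-N share at which adjusted means are evaluated, as the code already does for baseline titer.
- Tabulate GMT and GMR by dose and serostatus.

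This needs no new samples and no change in sample size. The cost is SAP wording, one degree of freedom, and an RMSE loss under 1% if there is no residual effect. No gain should be expected for vaccine-versus-placebo contrasts if the effect exists only in vaccinees.

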#### 219112 (MRNA CLINRES-001) Protocol Amendment 3 Final

Diagnosis of COVID-19 should be made in accordance with the World Health Organization [WHO, 2023] case definitions. Cases should be reported as AESIs or SAEs, and routine procedures for recording, evaluation, follow-up, and reporting of AESIs, and SAEs should be followed in accordance with the protocol-defined time periods.

\* TC1 is only for sentinel participants in each group in Part A.

\*\* Female participants of childbearing potential must perform a urine pregnancy test before the administration of the study intervention. For screening, if time allows, a serum pregnancy test can be done, in place of the urine pregnancy test, as per local requirements.

\*\*\* Physical examination, vital signs, and body temperature measurement at D1 will occur before vaccination.

+ Procedures apply to both suspected and convalescent visits for COVID-19.

Note: The double-line border following D15 indicates the analyses which will be performed on all data (i.e., data that are as clean as possible) obtained up to D15.

• Is used to indicate a study procedure that requires documentation in the individual eCRF.

• Is used to indicate a study procedure that requires documentation in the eDiary.

Interval	Planned visit interval	Allowed interval range
Screening $\rightarrow$ Visit 1 (D1)	1-14 days*	1-14 days
Visit 1 (D1) $\rightarrow$ TC1 (D2)	1 day	1 day
Visit 1 (D1) $\rightarrow$ Visit 2 (D8)	7 days	7-9 days
Visit 1 (D1) $\rightarrow$ Visit 3 (D15)	14 days	12-16 days
Visit 1 (D1) $\rightarrow$ Visit 4 (D31)	30 days	27-33 days
Visit 1 (D1) $\rightarrow$ TC2 (M3)	90 days	85-95 days
Visit 1 (D1) $\rightarrow$ Visit 5 (M6)	180 days	173-187 days

